In this study, the aim is to prospectively implement our NLP substance misuse classifier to examine its effectiveness in augmenting current practice that features physician referrals in hospitalized adult patients at Rush University Medical Center (RUMC).

STAFF

All work involving patient data will be performed at Rush and Rush staff will gain access to the Rush servers with approved credentialing and authentication by Rush IT. No data will be accessible to external investigators without a fully executed data use agreement and/or IRB approval / SMART IRB reliance agreement.

TRIAL SETTING AND PARTICIPANTS

This pragmatic, quasi-experimental (pre-post) study will be implemented at Rush University Medical Center across the surgical and medical wards. The study will target all adult hospitalized patients over a 24-month period (12 months of manual screen and 12 months under implementation of the NLP tool) and an additional 6-month follow-up for secondary outcomes. Currently, SUIT performs screening for patients identified from physician referrals between 8am-6pm and Monday-Friday and uses Epic (Epic Systems Corporation, Verona, Wisconsin) EHR.

METHODS AND MATERIAL

Overview:

We will use a quasi-experimental, interrupted time series (ITS) design to evaluate the longitudinal effects of the automated screening classifier compared to the manual screen approach at Rush. ITS offers several advantages in making use of our longitudinal data. Our analysis will model the trend in the outcome before the implementation of the automated screen, the change in the outcome that can be attributed to the automated screen and the difference between the slopes in the pre-period versus post-period. It is anticipated that no other interventions that may impact the study outcome will occur during the study period.

A comparison cohort from the manual screen period will extend from August 1, 2022 to July 31st, 2024. The day of switching on the automated screen will mark the start of the intervention period on August 1, 2023 and extend through July 31, 2024. This provides a 30-month total study period (12 months manual screening, and 12 months automated screen, and 6 months additional follow-up for secondary outcomes).

Approach:

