Option 2: Epic Best Practice Alert (if available at time of study roll out): The Rush IT Operations team is currently in the process of implementing a real-time NLP system to support clinical decision support tools such as our automated classifier. Our team will work with the Rush IT team to integrate the opioid classifier into health systems, using the HL7 interface. The real-time data feeds, including a cTAKES NLP pipeline will be incorporated using both the Rush Azure cloud computing environment and Epic's Nebula cloud computing environment. Ultimately, the modeling of notes data as data feeds into the opioid classifier will include the following protocol: (1) rendering clinical documents in HL7 exchange as input from the hospital encounter; (2) notes will be moved into Rush's HIPAA secure Azure environment; (3) run cTAKES in Azure cloud to generate set of CUIs; (5) application calls the ML algorithm microservice, which uses the set of CUIs from NLP to generate outputs. (6) cloud service associates the output into Epic's Nebula system for integration back into Rush Epic as a best practice alert. The diagram below is a draft schematic for the architecture:

Eligibility criteria:

Inclusion Criteria:

- Ages 18 years old to 89 years old
- Inpatient status during hospitalization

Exclusion Criteria:

- Cannot participate in the usual care SBIRT intervention

Study Outcomes:

While our prior aims validated the automated screener as a process measure, this study is examining the tool as an outcome measure to identify patients with substance misuse in practice using a pragmatic, quasi-experimental design. We hypothesize that the natural language processing algorithm can provide a standardized and interoperable approach for an automated daily screen on all hospitalized patients and provide better implementation fidelity for screening, brief intervention, and referral to treatment.

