The primary outcome is the count of patients who received the composite outcome of any of the following: naloxone dispensing [prescription, free kit from clinic, or order for home kit], medication assisted treatment [buprenorphine, methadone, naltrexone, acamprosate, gabapentin, disulfiram], addiction consult, referral to outpatient treatment, brief intervention/motivational interviewing for substance misuse. Each component will be indicated separately in the flowsheet for the encounter, along with the type of SUIT team involvement: formal consultation, curbside consultation, or supporting other service. The design is an interrupted time-series prospective observational study. [Time Frame: 30 months]

The secondary outcome is all-cause re-hospitalizations following 6-months from the Index hospital encounter. We will compare healthcare utilization outcomes in all patients between manual screen period and automated screen period controlling for all patient demographic and clinical characteristics. [Time Frame: 24 months of evaluation with 6 months follow-up for rehospitalization] Further exploratory outcomes include analyzing each component of the primary outcome separately: naloxone dispensing, medication assisted treatment, addiction consult, referral to outpatient treatment, brief intervention/motivational interviewing for substance misuse.

Analysis Plan:

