Overall approach: Demographic and clinical characteristics between the manual and automated screen periods will be examined using bivariate statistics. We will also perform descriptive analysis to examine the proportion of hospitalized patients with substance misuse who received any component of the composite outcome (naloxone dispensing, medication-assisted treatment, addiction consult, referral to outpatient treatment, brief intervention/motivational interviewing for substance misuse) within each month of the study period, and we will plot these proportions using mixed-effects logistic regression, with time (month of observation) modeled using restricted cubic splines. The primary analysis for aim 1 will consist of an interrupted time series approach utilizing autoregressive integrated moving average (ARIMA) models to determine the effect of the automated screener to the manual screen for this outcome. ARIMA models are preferable to alternatives such as segmented regression which may inadequately control for seasonality and autocorrelation in time series data. We will also perform sensitivity analyses to confirm the results of aim 1 using generalized linear mixed-effects models (GLMM) that include random intercepts to account for multiple index encounters over the follow-up time period and adjust for important patient demographics and clinical characteristics including: age, sex, race/ethnicity, insurance status, diagnosis, and comorbidities. GLMMs will also be used to analyze secondary endpoints.

Specific aim 1: First, we will plot the counts of hospitalized patients who received any component of the composite outcome to examine seasonality, trends, and outlying values. A transformation will be applied to stabilize the variance over time if data are heteroscedastic. Differencing will be applied to induce stationarity, such as a difference to account for linear trend ($d=1$, degree of non-seasonal differencing) and autocorrelation functions (ACF) will be plotted to verify stationarity. After differencing,

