ACFs and partial ACFs will be used to determine the orders of autoregression (AR) or moving average (MA) that will correct for the remaining autocorrelation. We hypothesize that the intervention will promote a step change (binary indicator for a level shift when intervention begins) and possibly a ramp effect (variable takes the value of 0 before the intervention and increases by 1 for each month following the beginning of the intervention). Fit statistics (AIC, BIC) and residual analysis (Ljung-Box test for white noise) will be used to identify a parsimonious and appropriate model based on AR/MA orders, differencing assumptions, and parameters for intervention impact (step, pulse, or ramp).

Specific aim 2: The number of hospitalizations in the 6 months following the index encounter will be regressed on time period of index hospitalization (manual screen or automated screen) and patient demographic and clinical characteristics using mixed-effects Poisson regression models. GLMMs with appropriate link and distributions specified will consider other follow-up utilization outcomes (e.g., costs, any encounter).

Power analysis:

A simulation study was designed to examine potential step effects in a non-inferiority design. In 2020, there were 95 ± 10 addiction consults per month and an autocorrelation AR(1) of $\phi=0.4$. Additionally, we performed silent testing of the automated screener in 2020 where it detected ~ 70 additional cases of substance misuse per month that did not receive consults by the usual care approach. We propose that a non-inferiority margin of 15 consults is acceptable and a step effect of 20 is a feasible goal with the implementation of automated screening. Assuming a similar consult rate of 95 ± 10 per month in this study's pre-period (July 2022-June 2023) and $\phi=0.4$, we have 80% power to detect a step effect of +20, resulting in 115 ± 10 consults per month in the post-period (July 2023-June 2024).

Data Elements:

RUSH EHR

The following electronic health record data elements will be included in the data sets used for analysis. Most data will be obtained through direct extraction of EPIC; however, some data may be computed from EHR data and obtained through the Rush Clinical Research Analytics team or transformed from EHR data by the research team (NLP mapped concepts from the text):

- MRN
- Address with Geocoding
- Census Tract Identifiers
- Encounter ID and type

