EHR data for adult (ages 18 and above) patients will be collected. The target study population is adult (ages 18 and above)- male or female – that were identified by the manual or automated screening for substance misuse at Rush University Medical Center. Additionally, patients meeting only the age criteria within the specified time-frame for the study may be included for analyses regardless of potential of or screening for substance misuse. Investigators at Rush University anticipate approximately 57,800 RUMC patients will be included in the analysis, based on preparatory research planning.

POTENTIAL RISKS & BENEFITS

The main risk to subjects is breach of confidentiality. All data is maintained electronically and stored on password-protected computers using secured servers with limited access maintained at Rush University Medical Center. For analysis, Rush will access a delimited file containing patient notes and then process the data, load the model, and make a prediction for each patient. The software will generate output in the

form of a delimited file linking each patient's unique identifier (such as MRN) to a prediction about the patient's alcohol, opioid, non-opioid, and polysubstance use statuses. All these activities will be performed locally within Rush's HIPAA-secure servers.

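### The analysis population is stated inconsistently, and one version of it would let each period's own screen select the cohort

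*Combined protocol and SAP*

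**What the plan says.** The combined protocol and SAP describes its population in several places, in two different ways.

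- **Screen-identified.** TYPE AND NUMBER OF SUBJECTS gives the target population as adults "that were identified by the manual or automated screening for substance misuse at Rush University Medical Center". It then says that patients meeting only the age criterion "may be included for analyses regardless of potential of or screening for substance misuse". Age there is 18 and above, with no upper limit.
- **All adult inpatients.** TRIAL SETTING AND PARTICIPANTS says "The study will target all adult hospitalized patients over a 24-month period". The eligibility criteria are age ("Ages 18 years old to 89 years old"), inpatient status and, as an exclusion, being unable to take part in usual-care SBIRT; no screen result is required. The consent-waiver section also covers all adults admitted to the inpatient wards.
- **Size.** The sentence after the permissive one expects that "approximately 57,800 RUMC patients will be included in the analysis".

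The outcomes differ in what they need from this definition. The primary outcome is a monthly count of patients receiving any component of the composite. The Overall approach also plans a descriptive analysis of "the proportion of hospitalized patients with substance misuse who received any component of the composite outcome", and a patient-level mixed model (GLMM) to confirm Aim 1, with no cohort named. For the secondary outcome, Study Outcomes says "We will compare healthcare utilization outcomes in all patients between manual screen period and automated screen period".

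The section on the classifier-based decision support ends the manual screening program on the day the automated screener starts.

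**The concern.** Because manual screening stops when the classifier starts, a population made up of screen-identified patients would be chosen by one instrument before the switch and by another after it. Cohort membership would then be a result of the intervention. If the new screen finds more or milder cases, the denominator grows. The treated proportion may fall while more patients are treated, and rehospitalization per identified patient may fall while nobody benefits.

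Three analyses are open to this to different degrees. The descriptive proportion is taken among patients with substance misuse, and the plan does not say how that status is determined in either period. The GLMM needs a defined set of encounters and has none; fitted in screen-identified patients, it could contradict the count it is meant to confirm. Aim 2 would be affected if the target-population sentence were applied in place of the all-patients statement.

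The permissive wording also leaves the choice between the two sets open until the data have been seen. The plan expects a rise in the proportion of patients with substance misuse who screen positive and receive intervention, so an undefined denominator bears on a result it means to report.

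**Working it through.** **1. Which population does the expected size fit?** Inputs: 57,800 patients (TYPE AND NUMBER OF SUBJECTS), 95 consults per month and about 70 further cases per month without consults (Power analysis), and misuse prevalence as high as 25% (scientific review).

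- 95 + 70 = 165 per month; 165 × 24 = 3,960, or 6.9% of 57,800.
- DURATION gives January 2018 to June 2024, which is 78 months: 165 × 78 = 12,870.
- 0.25 × 57,800 = 14,450 at most with misuse.

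The 165 is only a proxy for identified cases, but the gap is wide. The figure fits an all-inpatient set.

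**2. The monthly proportion in a screen-identified cohort.** The plan's goal is 95 + 20 = 115 consults per month. In silent testing "it detected ~ 70 additional cases of substance misuse per month" without usual-care consults. The plan does not say how many of these the manual screen had already identified, so the net addition *a* lies between 0 and 70. Let N0 be identified cases per month before the switch (not given; assumed). Consults stand in for the composite.

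Before: 95/N0. After: 115/(N0 + a). The proportion falls when a > N0 × (115/95 − 1) = 0.21 × N0. With a = 70, break-even is N0 = 70 × 95/20 = 332.5.

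| N0 (assumed) | Before | After, a = 0 | After, a = 35 | After, a = 70 |
|---|---|---|---|---|
| 120 | 79.2% | 95.8% | 74.2% | 60.5% |
| 200 | 47.5% | 57.5% | 48.9% | 42.6% |
| 300 | 31.7% | 38.3% | 34.3% | 31.1% |
| 400 | 23.8% | 28.8% | 26.4% | 24.5% |

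The same gain of 20 consults can appear as a rise or a fall, depending on two quantities that the plan does not give.

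**3. The same gain with an all-inpatient denominator.** Assume 57,800 spread evenly over 24 months: 57,800/24 = 2,408 per month. Then 95/2,408 = 3.9% becomes 115/2,408 = 4.8%. Over 78 months (741 per month) it is 12.8% to 15.5%. Both move with the count.

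**4. Aim 2, only if restricted to identified patients.** Assume that the 70 added cases have r times the rehospitalization rate of the others and that the intervention has no effect. The unadjusted period rate ratio is (N0 + 70r)/(N0 + 70).

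- N0 = 200, r = 0.5: 235/270 = 0.87; r = 0.75: 252.5/270 = 0.94.
- N0 = 120, r = 0.5: 155/190 = 0.82; r = 0.75: 172.5/190 = 0.91.

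The stated 80% power does not enter this point.

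**The case against.** A reader of the target-population sentence alone might infer that the screen under test decides who is eligible, so that the trial's main comparison is biased. The documents do not support that. Formal eligibility contains no screen result, two other sections describe all adult inpatients, and the expected size fits only that set. The primary outcome is a count without a denominator. The proportion is labelled descriptive. The Aim 2 population is stated as all patients, with adjustment for demographic and clinical characteristics that the ratios above ignore.

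Nor do the documents say that misuse status is known only from the period's screen. The data elements include diagnoses, ICD codes and concept identifiers from notes, and safety monitoring foresees patients known to the care team but missed by the screener. It would also be wrong to say that the proportion cannot rise: the table shows that it can.

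All of this stands, and it limits the point. It does not remove it. An intention inferred from a sample size is not a rule, having the data elements does not define misuse, and nothing names the GLMM cohort. If the target-population sentence were used as a filter, patients treated without being flagged would drop out differently in the two periods, and even the primary count could shift.

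**Conclusion.** The plan contradicts itself on its analysis population, and one of the two versions would let the intervention select the cohort. The primary count is sound if all eligible inpatients are used. The descriptive proportion and the confirmatory GLMM lack a cohort defined independently of the screen. Aim 2 is at risk only if the screen-identified definition displaced the all-patients statement.

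The size is conditional. In a screen-identified cohort the proportion falls once net added cases exceed about 0.21 times the assumed baseline. A restricted Aim 2 could show an unadjusted ratio of 0.87 to 0.94 at N0 = 200 with no true effect. These figures rest on an assumed N0, consults in place of the composite, and, for Aim 2, an assumed relative rate with all 70 cases newly identified. They show direction and scale and are not estimates of bias in this trial. The point should be fixed, but it does not undermine the primary analysis as most of the document describes it.

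**What to change.** Replace the target-population sentence and the permissive sentence after it with one set for both periods: all encounters meeting every listed eligibility criterion (age 18 to 89, inpatient status, and the SBIRT exclusion). Name that set for the primary count, the GLMM, Aim 2 and the main monthly proportion.

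If a substance-misuse subset is wanted, apply one definition identically in both periods. One option is the frozen classifier, at the same cut-off and note window, run on stored manual-period notes. State its limits: it is the same in both periods but is defined by the tool under test, and it omits cases found only by manual screening. Report patients identified by the period's own screen descriptively only.

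The cost is a wording change plus, for that option, one batch run. Concept identifiers from the notes are already among the data elements, and the screener was run silently in 2020. The drawback is dilution: in all inpatients the planned gain is a small change in proportion, as step 3 shows.
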